1.1 Trial schema

Figure 1 Trial schema

Interested volunteers complete online expression of interest questionnaire					
↓					
Pre-screening of initially eligible volunteers by recruiting site					
↓					
Time point	Group				
	1	2	3	4	5
Visit 1 Day 0	All participants: Consent, medical history and physical examination, observations (including height, weight, temperature), eligibility confirmation, randomization and vaccination				
	Blood sample: S-protein and exploratory subset T-cells	Blood sample: gE serology, CD4+ and exploratory subset T-cells	Blood sample: HAI and exploratory subset T-cells	Blood sample: HAI and gE serology and CD4+ subset	Blood sample: gE serology and CD4+ subset
	C19 + Placebo	RZV + Placebo	aQIV + placebo	RZV + aQIV	RZV + placebo
Participant completes diary for 7 days and reports any hospitalisations or concerns.					
Half of the participants in group 3 will end the study here					
Visit 2 Day 26 - 32	All participants: safety review.				
	1	2	3	4	5
	Blood sample: S-protein and exploratory subset T-cells	Blood sample: exploratory subset T-cells	Blood sample: HAI and exploratory subset T-cells	Blood sample: HAI	-
Visit 3 Day 56-60	All participants: safety review, temperature and vaccination.				
	1	2	3	4	5
	Blood sample: gE serology and CD4+ subset	Blood sample: S-protein	Blood sample: S-protein, gE serology and CD4+ subset	-	Blood sample: HAI
	RZV + Placebo	RZV + C19	C19 + RZV	RZV + placebo	RZV + aQIV
Participant completes diary for 7 days and reports any hospitalisations or concerns.					
Visit 4 Day 82-86	All participants: safety review.				
	1	2	3	4	5
	-	Blood sample: S-protein, gE serology and CD4+subset	Blood sample: S-protein	Blood sample: gE serology and CD4+ subset	Blood sample: HAI, gE serology and CD4+ subset
Visit 5 Day 112-116	All participants: safety review, temperature and vaccination*.				
	1	2	3	4	5
	-	-	-	-	-
	RZV	aQIV or placebo*	RZV	C19 or placebo*	C19 or placebo*
Participant completes diary for 7 days and reports any hospitalisations or concerns.					
Visit 6 Day 140-146	All participants: safety review.				
	1	2	3	4	5
	Blood sample: gE serology and CD4+ subset	-	Blood sample: gE serology and CD4+ subset	-	-
	aQIV*				

*these vaccinations will be given if the visit is taking place during the winter vaccination season, if not, a placebo injection will be given instead for visit 5.

2. Background & Rationale

Routine immunisation with herpes zoster vaccine (HZV) is recommended in the UK for adults on their 70th year.² HZV uptake is highest during influenza season. This higher uptake is thought to be due to opportunistic co-administration of HZV and influenza vaccine. HZV coverage ranges from 48.2% to 76.7% with the lowest coverage associated with the birth cohort who turned 70 in the 2020/21 season.³ The lower coverage is due to displacement of HZV vaccination by COVID-19-related disruption to health systems and vaccine rollout. Co-administration of HZV alongside COVID-19 vaccination may help prevent such displacement in the future. Up until May 2023 concomitant administration of RZV with either adjuvanted or COVID-19 vaccine (C19) was not recommended due to concern about misattribution of side-effects and limited experience with COVID-19 vaccines. The policy was updated in May 2023 to allow co-administration of COVID-19 vaccines with any vaccine. This was based on recent evidence supporting the acceptable safety profile of a COVID-19 vaccine with RZV and to improve timely protection and uptake.⁴ There is still a need however for safety data with co-administration of second dose of RZV as the adverse event profile differs between the doses and there is a lack of published data on the safety and immunogenicity of RZV and adjuvanted flu vaccine.

If, as anticipated, the COVID-19 vaccination becomes a routine vaccination, alongside influenza, then strategies to ensure uptake of other adult vaccines such as RZV, are needed. Vaccine co-administration is commonplace in the childhood immunisation programme and facilitates the uptake of vaccine. A similar strategy for adult vaccines could support vaccine uptake, however a better understanding of the impact and attitudes of multiple vaccination for both providers and those offered vaccine is needed to optimise this strategy.

In addition to the benefits that co-administration may provide for vaccine delivery, there may also be clinical benefits. Recent data suggest that both aQIV and RZV may reduce the incidence of severe COVID-19 disease. The mechanisms underlying potential cross-protection or vaccine synergy are unknown and comparative measurements of immune responses when these vaccines are given together and at separate times may help inform the design of vaccine delivery programmes and formulations.^{5,6}

Here we propose to evaluate the immunogenicity and safety of RZV co-administered with an mRNA COVID-19 vaccine or an adjuvanted influenza vaccine and describe immunological mechanisms underlying potential vaccine synergy and cross-protection and describe attitudes to co-administration.

3. Aims and objectives

The ZosterFluCov trial aims to evaluate whether RZV can be co-administered with an mRNA COVID-19 (C19) vaccine or an adjuvanted influenza vaccine (aQIV) without an unacceptable increase in reactogenicity or decrease in the immunogenicity of the COVID-19, influenza or RZV vaccines.

Co-Primary Objectives

Part A: Assessment of co-administration of COVID-19 and RZV

1. Immunogenicity, measured by S-binding total Ig, 1 month after COVID-19 mRNA reinforcing dose (Bivalent) vaccine for both strains included in the vaccine given alone compared to co-administration with RZV (1st or 2nd dose).

2. Immunogenicity of 2 doses of RZV vaccine, 1 month after the second dose, given alone, compared to co-administration with C19 with either 1st or 2nd dose of RZV.
3. Rate of grade 3 and 4 solicited systemic adverse reactions over 7 days after 1st and 2nd doses of RZV given alone compared to co-administration with Bivalent vaccine.

Part B: Assessment of co-administration of adjuvanted influenza vaccine and RZV

1. Immunogenicity, measured by haemagglutination inhibition assay, 1 month after adjuvanted influenza vaccine (aQIV) for 3 of the strains included in the vaccine; HAI influenza A H3N2, HAI influenza A H1N1 and HAI influenza B Victoria given alone compared to co-administration with RZV.
2. Immunogenicity of 2 doses of RZV vaccine when given alone, 1 month after the second dose compared to co-administration with aQIV with either 1st or 2nd dose of RZV.
3. Rate of grade 3 and 4 solicited systemic adverse reactions over 7 days after 1st and 2nd doses of RZV given alone compared to co-administration with aQIV.

Key Secondary Objectives

1. Cell-mediated responses to 2 doses of RZV, 1 month after the 2nd dose, given alone compared to co-administration with C19 vaccine with 1st or 2nd dose of RZV.
2. Exploratory evaluation of CD4+T-cells against COVID-19 after vaccination with RZV or aQIV in the CMI cohort.
3. S and N- protein immunoglobulin, before and 1 month after first vaccination in the exploratory immunology cohort.

4. Solicited systemic AEs over 7 days after 1st and 2nd doses of RZV given alone compared to co-administration with either C19 vaccine or aQIV.
5. Solicited local adverse reactions over 7 days after 1st and 2nd doses of RZV given alone compared to co-administration with either C19 vaccine or aQIV.
6. Solicited systemic AEs over 7 days after 1st doses of RZV given alone compared to co-administration with either C19 vaccine or aQIV.
7. Solicited systemic AEs over 7 days after 2nd doses of RZV given alone compared to co-administration with either C19 vaccine or aQIV.
8. Grade 3 and 4 SSR after 1st RZV dose in group 1 (day 56), 2 and 5 (day 0) compared to grade 3 and 4 SSR after 1st dose of RZV with C19 vaccine in group 3 (day 56)
9. Grade 3 and 4 SSR after 2nd dose of RZV in group 1, 3 (day 112) and 4 (day 56) compared to grade 3 and 4 SSR after 2nd dose RZV with C19 vaccine in group 2 (day 56).
10. Grade 3 and 4 SSR after 1st dose RZV in group 1 (day 56), 2 and 5 (day 0) compared to grade 3 and 4 SSR after 1st dose of RZV with aQIV in group 4 (day 0).
11. Grade 3 and 4 SSR after 2nd dose of RZV in group 1, 3 (day 112) and 4 (day 56) compared to grade 3 and 4 SSR after 2nd dose RZV with aQIV in group 5.
12. Days off work (for participants in employment) due to vaccine related AEs associated with different schedules under study over a period of 140 days .
13. Quality of life score over the 7 days after 1st and 2nd doses of RZV given alone compared to co-administration with either BNT162b vaccine or aQIV.
14. Unsolicited AEs up to 30 days after 1st and 2nd doses of RZV given alone compared to co-administration with either C19 vaccine or aQIV.
15. Serious adverse events and AEs of special interest including potential immune mediated disorders (pIMD) from after first vaccination until the study end.

16. Describe participant and study nurse attitudes to vaccine co-administration.

4. Primary and secondary outcomes

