4.1 Primary outcome

Part A: Assessment of co-administration of COVID-19 and RZV

Co-Primary Endpoints

1) Immunogenicity of C19

Anti-S protein Ig concentrations expressed as Geometric Mean Concentrations (GMCs) for both strains in C19 vaccine/RZV (first or second dose, groups 2 & 3) and C19 vaccine alone (group 1), will be used to calculate between group ratios expressed a geometric mean ratio (GMR), at 1 month after vaccination with C19 vaccine.

2) Immunogenicity of RZV

Anti-gE Ig concentrations expressed as GMCs after co-administration of C19 vaccine/RZV (first or second dose) and RZV alone, 1 month after 2nd dose of RZV, and between-group ratios expressed as GMRs.

Success criteria:

Part A of the trial will be classified as a success if both of the following meet the success criteria:

- 1) The combined administration of C19 vaccine and RZV (first or second dose) will be considered non-inferior to C19 vaccine alone if the lower limit of the 95% confidence interval for the (GMR) of anti-S protein Ig concentrations exceeds 0.67, the standard WHO non-inferiority margin for recommendation of new vaccines.⁷, AND

2) The combined administration of C19 vaccine and RZV (first or second dose) will be considered non-inferior to RZV alone if the lower limit of the 95% confidence interval for the GMR of Anti-gE Ig concentrations exceeds 0.67.

3) Safety of RZV

The rate of grade 3 and 4 solicited systemic adverse reactions (Table 2) after C19 vaccine/RZV (first or second dose, groups 2 and 3) and RZV alone 7 days after vaccination (groups 1-5) This is a descriptive outcome.

Table 2 Solicited AEs collected on post vaccination diary cards

Systemic solicited AEs
Fatigue
Fever
GI symptoms†
Headache
Myalgia
Shivering

†Gastrointestinal symptoms include nausea, vomiting, diarrhoea and/or abdominal pain

Note: The above AEs are assumed to be related and will be classed as adverse reactions.

Part B: Assessment of co-administration of adjuvanted influenza vaccine and RZV

Co-Primary Endpoints

1) Immunogenicity of aQIV

HAI titres expressed as GMCs in aQIV/RZV (first or second dose, groups 4 & 5) and aQIV alone (group 3) will be used to calculate between group ratios, expressed as GMR at one month after aQIV vaccination.

2) Immunogenicity of RZV

Anti-gE Ig concentrations expressed as GMCs after co-administration of aQIV/RZV (first or second dose) and RZV alone, 1 month after 2nd dose of RZV, and between-group ratios expressed as GMRs.

Success criteria:

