5.8.4 Visit 2: Safety review and blood sampling

At this visit, approximately 4 weeks after visit 1, participants will undergo the following:

- Safety review to assess for any serious adverse events
- Review and reconciliation of diary card data submitted
- Assessment for local and systemic adverse reactions and events and medical history since visit 1
- Provide blood sample for assessment of COVID-19, influenza vaccine immunogenicity
- Provide blood sample for exploratory immunology analysis*
- Participants in group 3 who will not be invited to continue the study will be informed and permission sought to follow up to resolution any clinically significant adverse events after the end of trial participation

5.8.5 Between visit 2 and visit 3

In the period between the second visit and the third visit approximately 4 weeks later participants will be required to:

- Report any hospitalisation as soon as is practically possible using the emergency 24-hour telephone number provided
- Report any other urgent medical concerns using the trial centre emergency procedures
- Report any unsolicited adverse events on the electronic diary card

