12.7 Expenses

Volunteers will be compensated for their time, the inconvenience of having blood tests and procedures, and their travel expenses. The total amount compensated will depend on the exact number of visits, and whether any repeat or additional visits are necessary. For all trial visits participants will be compensated up to £45 per visit (total compensation for completing trial would be £90 for a subset of participants in groups in group 3 and up to £270 for all other participants).

13. Statistics

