13.1 Sample size calculation

Sample size calculations have been performed to test all primary immunogenicity objectives in both part A and part B of the trial. All sample size calculations were performed using the SSI module in Stata.⁹

Part A: Assessment of co-administration of COVID-19 vaccine and RZV

We hypothesise that (1) immunogenicity (anti-S protein Ig concentrations, both Original and Omicron strains) of concomitant administration of C19 and RZV (first or second dose) will be non-inferior to C19 alone, and (2) immunogenicity (anti-gE Ig concentrations) of concomitant administration of RZV (first or second dose) and C19 will be non-inferior to RZV alone.

The power calculations to test hypotheses in part A are provided in Table 10.

Table 10 Sample size estimates for part A

Outcome	Sample size excluding 10% inflation for dropout	SD (log10 scale)	Assumed true GMR	Non-inferiority margin (log10 scale)	Power for each outcome	Conjunctive power for part A
Anti-S Ig	95	0.35	1	0.174	92.9%	80.1%
Anti-gE Ig	95	0.35	1	0.174	92.9%	

A sample size of 106 per group will provide 80% power to test all part A hypotheses using a 2.5% one-sided significance level and allowing for 10% dropout.

Part B: Assessment of co-administration of adjuvanted influenza vaccine and RZV

We hypothesise that (1) immunogenicity (for 3 of the strains included in the vaccine; HAI influenza A H3N2, HAI influenza A H1N1 and HAI influenza B Victoria) of concomitant administration of aQIV and RZV (first or second dose) will be non-inferior to aQIV alone, and (2) immunogenicity (anti-gE Ig concentrations) of concomitant administration of RZV (first or second dose) and aQIV will be non-inferior to RZV alone.

The power calculations to test hypotheses in part B are presented in Table 11.

Table 11 Sample size estimates for part B

Outcome	Sample size excluding 10% inflation for dropout	SD (log10 scale)	Assumed true GMR	Non-inferiority margin (log10 scale)	Power for each outcome	Conjunctive power for correlated outcomes (HAI)*	Conjunctive power for part B
HAI influenza A H3N2	216	0.45	1	0.174	98.0%		
HAI influenza A H1N1	216	0.54	1	0.174	91.8%	80.7%	80.6%
HAI influenza B Victoria	216	0.57	1	0.174	88.7%		
Anti-gE Ig	216	0.35	1	0.174	99.93%	-	

* Estimated using correlation matrix from ComFluCOV HAI data; conjunctive power for HAI outcomes was calculated using R.

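### The trial schema ends participation for half of Group 3 before visit 2, but the rest of the protocol needs those participants at visit 2 for the co-primary HAI sample

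*Protocol*

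**What the plan says.** Figure 1 (Protocol, 1.1) gives the exit of half of Group 3 its own row, "Half of the participants in group 3 will end the study here". The row follows the visit 1 vaccination and 7-day diary and precedes the visit 2 block, which is where the Group 3 HAI sample is listed.

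Other parts of the protocol place the exit at visit 2:

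- Section 5.8.4, which describes visit 2, includes "Provide blood sample for assessment of COVID-19, influenza vaccine immunogenicity" and then "Participants in group 3 who will not be invited to continue the study will be informed". The leavers are therefore present at that visit.
- Section 12.7: "total compensation for completing trial would be £90 for a subset of participants in groups in group 3", at up to £45 per visit.
- The synopsis (Table 1) sets the influenza serology cohort at 720, with 240 randomised to each of Groups 3, 4 and 5. It limits only progression to the second and third vaccination time points, to 120 of Group 3.
- Table 11 (13.1) assumes 216 evaluable per group for each HAI strain.

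Section 4.1 defines the HAI comparison: "aQIV alone (group 3) will be used to calculate between group ratios, expressed as GMR at one month after aQIV vaccination". Group 3 receives aQIV at day 0 (Table 3), so its endpoint sample is the visit 2 draw.

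**The concern.** Group 3 is the only aQIV-alone arm, and visit 2 provides its only HAI endpoint sample. A participant released where the schema row stands would have a baseline titre and no primary endpoint. The row concerns 120 of the 240 controls.

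The remaining text does not state the exit point outright. No sentence says that all 240 Group 3 participants attend visit 2. Section 10 defines an individual's end of trial only as completing visit 6 or loss to follow-up, which gives this subset no exit point. About 15 sites (12.2) will use the schema as a working summary, and a day 28 sample missed at a site cannot be recovered.

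**Working it through.** **Where the exit falls**

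| Source | Implied exit for the Group 3 leavers |
|---|---|
| Figure 1 row | before visit 2 |
| 5.8.4 | at visit 2, where blood is drawn |
| 12.7 | £90 / £45 = 2 visits, so visits 1 and 2 |
| Table 1, influenza cohort | 720 = 3 × 240, so all of Group 3 is counted |
| Table 11 | 216 = 0.9 × 240, so all of Group 3 less 10% dropout |

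**Inputs.** SD on the log10 scale: 0.45 (H3N2), 0.54 (H1N1), 0.57 (B Victoria). Margin 0.174, true GMR 1, one-sided 2.5%, 216 evaluable per group. All are from 13.1. The correlation between strains is not given in the protocol, so it is an assumption here.

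**Formula.** Power = Φ(0.174 / (SD × √(1/n₁ + 1/n₂)) − 1.96).

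**Step 1: reproduce Table 11 (216 v 216).** √(2/216) = 0.09623.

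- H3N2: 0.174/0.04330 = 4.018, power 98.0%
- H1N1: 0.174/0.05196 = 3.349, power 91.8%
- B Victoria: 0.174/0.05485 = 3.172, power 88.7%

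All three match. Conjunctive HAI power from a trivariate normal is 79.8% at correlation 0 and 80.7% at a common correlation of 0.18, which is the stated figure. Multiplying by the anti-gE power gives 0.807 × 0.9993 = 80.6%, the stated Part B power.

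**Step 2: worst case under the schema row.** If all 120 leavers go before visit 2, 120 controls remain, and 0.9 × 120 = 108 are evaluable. √(1/108 + 1/216) = 0.11785.

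- H3N2: 0.174/0.05303 = 3.281, power 90.7%
- H1N1: 0.174/0.06364 = 2.734, power 78.1%
- B Victoria: 0.174/0.06718 = 2.590, power 73.6%

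Conjunctive HAI power is 52.1% at correlation 0, 55.1% at 0.18 and 60.9% at 0.5. It cannot exceed the weakest strain, 73.6%, whatever the correlation.

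**Step 3: sensitivity**

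| Case | Evaluable | Conjunctive, correlation 0 | Ceiling |
|---|---|---|---|
| All leavers released early | 108 v 216 | 52.1% | 73.6% |
| As above, no dropout among the 120 who stay | 120 v 216 | 57.1% | 76.5% |
| As the first row, Groups 4 and 5 pooled | 108 v 432 | 65.3% | 81.0% |
| Half the leavers released early (0.9 × 180 = 162) | 162 v 216 | 70.1% | 83.6% |

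The last row uses the same formula with √(1/162 + 1/216) = 0.10393, which gives 96.1%, 87.3% and 83.6% by strain. Each 10 leavers lost remove 10/240, about 4%, of the planned control arm.

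**The case against.** The best defence is that this is one misplaced row and not a competing exit rule. Section 5.8.4 is the only text that says when leavers are told, and it says visit 2. The payment, the cohort of 720 and Table 11 agree with it. The schema's own visit 2 block lists the Group 3 HAI sample without restricting it to half, and Table 4 schedules influenza-subset serum at visit 2. Sites receive protocol training (14.2.1), and the trial management group reviews adherence to visits centrally (14.2.2), so missed day 28 visits should surface early. Most of this stands. The unrestricted schema cell is weaker evidence than it looks, because the Group 3 cells from visit 3 onward are equally unrestricted although only half of the group remains by then.

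A reader might infer that Part B is underpowered, or that Table 11 is wrong. The documents do not support that: Table 11 reproduces exactly, and nothing besides the schema row plans for 108 controls.

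The size of the loss is also open to challenge. The 55% rests on a single common correlation fitted to one stated figure. The 108 applies the full 10% dropout by day 28, whereas 12.6 expects less than 5% over the whole study. Pooling Groups 4 and 5 would soften the loss, although the stated per-strain powers match 216 v 216 and not a pooled comparison. These points argue for quoting a range. They do not reverse the direction: with all leavers released early, only pooling combined with near-perfect correlation would reach 80%.

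Finally, the row's position was read from extracted text. It stands as a separate row between the two visit blocks, but it should be checked against the laid-out figure.

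**Conclusion.** The schema row contradicts 5.8.4 and 12.7 and does not fit the cohort of 720 or Table 11. It is the outlier. The design and the sample size calculation are sound if the leavers attend visit 2. The row still matters because it gives sites a wrong operational instruction about the only HAI endpoint sample in the only aQIV-alone arm.

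The power loss is conditional on sites following the row. The worst case leaves conjunctive HAI power at no more than 73.6%, against the stated 80.7%. That ceiling uses the protocol's SDs, margin and 10% dropout and needs no correlation assumption; the values of 52% and 55% do need one. If only some sites follow the row, the loss is smaller. Anti-gE power is unaffected, because the leavers receive no RZV in the trial. The correction is worth making, since it is cheap and the lost samples would not be retrievable.

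**What to change.** Reconcile Figure 1 with 5.8.4. Move the schema row below the visit 2 block and reword it along these lines: *After the visit 2 (day 26-32) HAI blood sample and safety review, half of the participants in Group 3 will end the study.* A matching sentence in 5.8.2, saying that all 240 Group 3 participants attend visit 2, is optional. If 5.8.2 is edited, its figure of 129 continuing Group 3 participants should be reconciled with the 120 in the synopsis, which is a separate discrepancy.

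The cost is one figure row and at most one sentence. The sample size and analysis do not change.

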
Dosing* schedule
	
The dose of RZV is 0.5ml. The vaccine should be administered intramuscularly, preferably in the deltoid muscle. Shingrix is presented as 2 vials, one containing the antigen powder and the other adjuvant in suspension. Shingrix must be reconstituted prior to administration. Two doses need to be administered, at the interval of 2-6 months between the doses.
	
The dose of Comirnaty original/omicron BA.4-5 vaccine is 15ug original and 15 µg omicron contained in 0.3ml of diluted vaccine. The vaccine should be administered intramuscularly into the deltoid. Each pack of the Comirnaty original/omicron BA.4-5 vaccine contains 195 vials with 6 doses per vial. The vaccine should be stored out of the light prior to use.
	
The dose of aQIV contains 15µg of each strain in a 0.5ml dose. The vaccine is administered by intramuscular injection with the preferred site being the deltoid muscle of the upper arm. The vaccines come in pre-filled syringes with or without needles. The vaccine should be allowed to reach room temperature before use.

-------------------------	--	--	---

Regulatory status	Marketing authorisation from the MHRA from 1 st January 2021	Marketing authorisation from the MHRA from 21 st December 2020, renewed on 9 th November 2022.	Marketing authorisation from the MHRA from 7 th September 2021.
Preparation and labelling	There will not be investigational medicinal product (IMP) labelling for this trial. Products will be used as supplied by the manufacturer (as for national supply) and blinding will be performed as per section 5.6.		
Drug storage and supply**	Stored at 2-8°C and in the original package to protect from light. Once reconstituted the vaccine should be used immediately, if not used immediately it should be stored at 2-8°C for no longer than 6 hours.	Stored at -90°C - 60°C. Once thawed, the vaccine may be stored for 10 weeks at 2-8°C	Stored at 2-8°C.

* Dose modifications are not expected to occur.

*** Vaccines and placebo will be stored in accordance with manufacturers' recommendations, in accordance with GCP pharmacy department standard operating procedures (SOPs).*

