6.10 Duration of treatment period

The duration of the treatment commences when the participant receives their first vaccines as per randomisation and concludes one month after visit 5. For each participant this will be a total of approximately 5 months.

7. Data collection

Each participant will be assigned a unique trial number. Administrative data recorded on paper relating to the participant will be stored securely. Staff with authorisation to make changes to the trial records on the trial database, will be listed on the site delegation log.

Baseline data will be collected after written informed consent. Volunteers will be contacted by an authorised member of the local research or direct care team (as specified in the delegation log) who will provide the opportunity to understand the nature, significance, implications and risks of the trial so that they may make an informed decision if they should take part. If the patient decides to take part the member of the local research or direct care team will obtain informed consent.

Data collection will include the following elements:

- a) A log of all volunteers who express interest in joining the trial and pass the pre-screening eligibility checks.
- b) Volunteers assessed against the full eligibility criteria and, if ineligible, reasons for ineligibility.
- c) Consent information collected prior to randomisation for all participants.
- d) Baseline information (e.g., medical history and assessments) collected for all participating patients.
- e) Data collected from participant diaries completed throughout their participation in the trial.
- f) Data collected at trial visits.
- g) Data derived from analyses of blood samples.

Impact of life measures

This will be assessed using the EQ-5D health survey which participants will be asked to fill in electronically through the platform used for trial management. If participants do not have access to an internet connected device, they will have the option to complete a paper EQ-5D questionnaire.

Diary cards will capture missed time from work by employed participants and caregivers.

8. Integrated Qualitative Research

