12.2 Planned recruitment rate

Anticipated rate of enrolment:

We will recruit 960 participants at approximately 15 sites over a 6 month period. For the first 50 participants recruited to Groups 4 and 5 there will be real time safety monitoring. Once the first 50 participants in Groups 4 and 5 reach visit 3, then a safety review will take place and will include data up to 30 days after the second vaccination point. Recruitment to the study will continue during the safety review but will pause if there are any safety concerns.

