16.1 Sponsor approval

Any amendments to the trial documents must be approved by the sponsor prior to submission to the HRA, REC and MHRA as applicable.

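### Visit windows are counted from Day 0, so an in-window RZV interval can be 52 days in groups 1 and 3, and dose-to-sample intervals differ between compared arms

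*Protocol*

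**What the plan says.** Figure 1 (section 1.1) gives the windows as "Visit 2 Day 26 - 32", "Visit 3 Day 56-60", "Visit 4 Day 82-86" and "Visit 5 Day 112-116", with visit 6 at days 140-146. The window row of Table 4 (section 5.8) repeats the same ranges. Neither place moves a later window when an earlier vaccination visit falls late.

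Table 3 (section 5.5) places the RZV doses at days 56 and 112 in groups 1 and 3, and at days 0 and 56 in groups 2, 4 and 5. For RZV, Table 5 (section 6.1) states: "Two doses need to be administered, at the interval of 2-6 months between the doses".

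Section 4.1 defines all the co-primary immunogenicity endpoints at one month after the relevant dose. Sections 5.8.8 and 5.8.12 describe visits 4 and 6 as about four weeks after the preceding visit, without day limits. Section 5.8.14 requires discussion with the coordinating centre and chief investigator only when a visit falls outside its window.

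**The concern.** A window counted from Day 0 controls time since enrolment. What matters for dosing and for the immunogenicity endpoints is the time since the last dose, and that is the difference between two visit days, each free to move. Two things follow.

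- **Dosing.** A site that keeps to both windows can give the second RZV dose too early by the protocol's own Table 5, and no check is triggered because neither visit is out of window. This can happen only in groups 1 and 3. Group 1 is the only arm given both RZV doses without another active vaccine, so the natural anti-gE control may have a shorter dose interval than groups 2, 4 and 5.
- **Sampling.** The visit at which an arm is sampled depends on its allocated schedule. A difference in permitted sampling interval between visits is therefore a difference between arms, and randomisation does not balance it. In the affected comparisons, the ratio sets titres measured over one range of days after the dose against titres measured over another.

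**Working it through.** **Inputs** (Figure 1 and Table 4): V1 day 0; V2 days 26-32; V3 days 56-60; V4 days 82-86; V5 days 112-116; V6 days 140-146. Doses and samples by group are from Figure 1 and Table 3.

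**Nominal schedule.** RZV doses are 56 - 0 = 56 or 112 - 56 = 56 days apart. Samples fall 28 - 0, 84 - 56 and 140 - 112 = 28 days after the dose. On target days every arm is aligned; the problem lies in the windows alone.

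**Formula.** Shortest interval = earliest later day - latest earlier day. Longest interval = latest later day - earliest earlier day.

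**RZV dose 1 to dose 2**

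| Groups | Visits | Shortest | Longest |
|---|---|---|---|
| 1, 3 | V3 to V5 | 112 - 60 = 52 | 116 - 56 = 60 |
| 2, 4, 5 | V1 to V3 | 56 | 60 |

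Of the 5 × 5 = 25 permitted V3/V5 day pairs, 10 give fewer than 56 days. An interval of 52 days is 4 short of eight weeks and 7-10 short of two calendar months (59-62 days). For any V3 day from 56 to 60, adding 56 gives day 112 to 116, so an interval of at least 56 days is always available in window.

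**Dose to sample**

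| Visits | Shortest | Longest | Midpoint | Primary samples |
|---|---|---|---|---|
| V1 to V2 | 26 | 32 | 29 | anti-S group 1; HAI groups 3, 4 |
| V3 to V4 | 82 - 60 = 22 | 86 - 56 = 30 | 26 | anti-S groups 2, 3; HAI group 5; anti-gE groups 2, 4, 5 |
| V5 to V6 | 140 - 116 = 24 | 146 - 112 = 34 | 29 | anti-gE groups 1, 3 |

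At V4, 10 of 25 permitted pairs fall below 26 days, the lower limit at V2. At V6, 3 of 5 × 7 = 35 pairs fall below 26 days and 3 exceed 32. These are counts of permitted combinations, not expected frequencies.

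**Primary pairs**, taking group 1 as the RZV-alone control:

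- Different ranges: anti-S 2 v 1 and 3 v 1; HAI 5 v 3; anti-gE 2 v 1, 4 v 1 and 5 v 1 (6 pairs).
- Same range: HAI 4 v 3 and anti-gE 3 v 1 (2 pairs).

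All primary V4 samples belong to co-administration arms. In the six unmatched pairs the midpoint of the co-administration arm's range is 29 - 26 = 3 days earlier than the control's.

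**Illustrative size.** The protocol gives no titre kinetics. Suppose titres decline with a half-life h of 30 to 90 days. A difference of d days then changes the ratio by a factor 2^(d/h):

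- d = 3 (midpoints): 1.07 at h = 30 and 1.02 at h = 90. That is 0.030/0.174 = 17% and 0.010/0.174 = 6% of the log10 margin.
- d = 32 - 22 = 10 (opposite extremes): 1.26 and 1.08, or 58% and 19% of the margin.

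If titres were still rising at one month, the direction would reverse.

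**The case against.** The strongest reply is that Table 5 is also binding. A site must satisfy both tables, and a compliant day always exists, so the windows do not force a breach. That is true, and the shortfall against the planned 56 days is at most 4 days. But sites schedule by the window row, and nothing in the protocol flags a visit that is in window yet too close to the previous dose.

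A second reply is that the text places visits 4 and 6 about four weeks after the preceding visit, which shows a common target. It does, but without limits it does not constrain the day.

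A third is that the count of 6 in 8 assumes arm-by-arm contrasts with group 1 as the RZV-alone control, neither of which section 4.1 spells out. The count does rest on that reading. Pooling the co-administration arms would not help: each pooled group (2 with 3, or 4 with 5) includes at least one arm sampled at V4, while its control is sampled at V2 or V6.

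Finally, the effect is likely to be small. The 10-day extreme would need whole arms to sit at opposite window edges, and there is no reason to expect that. The SAP may also deal with actual sampling days. This limits the importance of the sampling point, but analysis cannot lengthen a dose interval already given.

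**Conclusion.** The concern holds. Fully compliant visits allow an RZV interval of 52 days in groups 1 and 3, below the stated 2-6 months whether two months means eight weeks or calendar months. Read as calendar months, even the planned 56 days falls short in every group (by 3-6 days), so the shortfall specific to these two groups is up to 4 days.

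Permitted dose-to-sample intervals differ in 6 of 8 primary pairs under the arm-by-arm reading with group 1 as anti-gE control, and in every primary contrast if arms are pooled. The interval arithmetic is certain. The effect on the ratios is probably small, and the protocol does not allow it to be sized or signed. This is a scheduling weakness worth correcting, not a threat to the trial's main conclusions. The sample size is unaffected.

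**What to change.** In Figure 1 and Table 4, count the later windows from the actual preceding vaccination:

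- **Visit 4:** 26-32 days after the visit 3 dose, i.e. days 56 + 26 = 82 to 60 + 32 = 92.
- **Visit 5:** 56-60 days after the visit 3 dose and never fewer than 56, i.e. days 56 + 56 = 112 to 60 + 60 = 120.
- **Visit 6:** 26-32 days after the visit 5 dose, i.e. days 112 + 26 = 138 to 120 + 32 = 152.

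RZV intervals are then 56-60 days in all groups, and all primary post-dose samples fall at 26-32 days. Stating in Table 5 that two months means 56 days would be a useful clarification, though not essential.

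The latest visit 6 day moves from 146 to 152, so follow-up is at most 6 days longer and section 6.10 still fits: "For each participant this will be a total of approximately 5 months". No visits, samples or participants are added. The cost is a protocol amendment, which under section 16.1 "must be approved by the sponsor prior to submission to the HRA, REC and MHRA as applicable", and its implementation at about 15 sites (section 12.2). If enrolment has already begun, earlier and later participants would follow different windows, and the report should say so.
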